**Cluster Randomized Trial of a School-Based Program to Prevent Teen Dating Violence**  
**NCT02909673**  
**7/21/20**

**Cluster Randomized Trial of a School-Based Program to Prevent Teen Dating Violence**  
**[name]. – Principal Investigator**

**Study Protocol**

**Purpose of Research:** The purpose of this NIH funded study is to evaluate the new and enhanced middle school version of *Fourth R*, a healthy relationships and prevention program previously shown to be effective in reducing risky behaviors and improving relationships among high school students.

**Specific Aims:** The primary aim is to determine whether *Fourth R* reduces students' teen dating violence (TDV), as indexed by less perpetration and victimization of physical, sexual, and psychological TDV, relative to students in control schools. The secondary aims are to determine whether *Fourth R*, relative to control, (1) improves students' emotional well-being, and increases their acquisition and use of healthy relationship skills, as indexed by improved problem-solving, communication, and conflict resolution skills and (2) ameliorates the modifiable cognitive and behavioral correlates associated with the perpetration and victimization of TDV, as indexed by fewer attitudes justifying dating violence, decreased substance use, decreased risky sexual behavior, decreased fighting and bullying, increased school connectedness, improved academic performance, and decreased psychological symptoms. Pre-specified differences by gender and ethnicity will be examined, as well as the acquisition and utilization of various program components.

**Research Design:** This five year study is a school-based cluster randomized trial (experimental design) of the middle school version of *Fourth R*, where students receiving the curriculum will be compared to students receiving usual health classes. Outcomes will be assessed at baseline and at 12, 24, and 36 months post intervention.

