**Sampling Design and Rationale:** We will recruit 24 middle schools in the Houston area for the study. A cluster-randomized trial will be used to assign the 24 participating middle schools (i.e., clusters) to the intervention (n=12) or control (n=12 as usual health classes) condition. Students (N=3,000) in these schools will be the unit of analysis and will be studied prospectively to determine the program's impact by comparing intervention students with control students. Outcomes will be assessed at baseline (when students are in 7th grade), and at 12-, 24-, and 36-months post-intervention, when students are in 8th, 9th, and 10th grade, respectively. To minimize school disruption, only the 1-year follow-up survey will be conducted in schools; the 2- and 3-year follow-up will be conducted via a web-based survey. The primary hypothesis is that intervention students will have significantly lower prevalence of physical, psychological, and sexual TDV perpetration and victimization than control students. The secondary hypothesis is that intervention students will have better healthy relationship skills (problem-solving, communication, conflict resolution), higher levels of school connectedness, better decision-making with respect to substance use and risky sexual behavior, better academic performance, and better mental health and well-being than control students.

**Recruitment:** The research team will recruit in 7th grade health classes at participating schools. A multi-method approach will be used for recruitment and to obtain parental permission. First, with district and school approval, research staff will include parental consent forms in the beginning-of-the-semester packets that are sent home with all students and parents will be asked to review, sign, and return. All consent materials will be provided in English and Spanish. Please see enclosed letter to parents, parent permission form, and student assent form. Second, research staff will actively follow up with "non-respondents" via phone and email. Third, to reach students who do not return a parental permission form, research staff will describe the purpose, design, and enrollment criteria to 7th graders

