Implementing teachers will be asked to complete curriculum monitoring (fidelity) and attendance sheets. Research staff will follow up with teachers to ensure these are completed. The site coordinator at each school will collect forms from teachers. With district and principal approval, research staff will attend 10% of the lessons delivered by each facilitator. Standardized checklists used by *Fourth R* staff that list main points and activities of each lesson will be utilized. Other observations will include percentage of time teachers use interactive instructional techniques, student behavior, deviations from the curriculum, and class size.

**Data Collection Procedures:** Students will be asked to complete paper/pencil surveys or web-based surveys hosted on a secure server (paper/pencil surveys will be completed when computers are unavailable). Prior to participating in the baseline survey, students will receive information about the study, what will be asked of them over the study period, and how their confidentiality will be protected. If they choose to participate in the survey, students will complete an assent form (parental permission will have already been obtained). Baseline and the 1-year follow-up will be conducted in the schools using paper and pencil surveys or school computers for web-based surveys during regular class time (paper/pencil surveys will be completed when computers are unavailable). We will employ the services of the Survey Research Division (SRD) at the University of Washington (UW) to assist with participant retention and the follow-up assessments. A majority of students will complete the 1-year follow-up survey in school, and any remaining students will complete the survey outside of the school setting via a mixed-mode approach (web, telephone, and paper surveys). Because participants will have transitioned from middle schools to high schools, the 2- and 3-year follow-ups will be done outside of the school setting via the mixed-mode approach. Students will receive a \$5 gift card for completing the baseline assessment, \$10 for completing the 1-year follow-up, and \$20 for the 2-year and 3-year follow-ups.

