Prior to the 1-year school-based follow-up assessment, SRD will confirm that participants are attending the school and conservatively estimate that approximately 80% will be at the same school. For the remaining 20%, as well as for the 2- and 3-year follow-up assessments, SRD will take various steps in locating and scheduling participants for the follow-up survey, including calling, texting, and

emailing. If these methods are unsuccessful, SRD will attempt to contact participants using the following methods (in successive order): call and text them at all available numbers; securely message them via social media; contact their relatives and friends, as approved by the participant; and mail them certified letters with return-to-sender envelopes. If all contact attempts fail, SRD will locate them through access to their online database and search firms. We have partnered with SRD in previous longitudinal studies with great success.

A lottery strategy will be implemented during the 2nd follow-up (9th grade) survey period and the 3rd follow-up (10th grade) survey period. This strategy has been successfully implemented on similar studies and has served to build enthusiasm among survey participants. In addition, all students who complete the survey will be offered 1 hour of high school volunteer service hours. We will send a certificate of completion to all participants who complete the survey by either mail or email and participants may present this certificate to their school for approval of volunteer service credit.

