To initiate the lottery strategy, we will send a notice to all participants, including those who have already completed their survey. There are 2 versions of the notice: (A1) tells those who have completed the survey that their name will be entered in the drawing, and they need to do nothing else to qualify for this opportunity; (A2) informs those who have not yet completed the survey that their name will be entered into the drawing if they complete their survey by the specified lottery deadline. The deadline is to be determined based on approval and will give participants sufficient notice and time to complete the survey. The notices will be either mailed or emailed to participants, depending on the best contact method we have for each participant. Study participants who have completed their survey by the deadline will be entered into a drawing for a \$100 e-gift card. There will be 10 participants chosen to each win a \$100 e-gift card. Winners will be chosen at random from all completed surveys by the lottery deadline. The drawing will be held within 2 business days after the deadline and e-gift cards for the winners will be emailed within 5 business days of the deadline. Winning participants will be notified by phone. A lottery conclusion notice will be emailed/mailed to all lottery participants once winners are randomly selected.

Implementing the lottery is an important participant retention strategy in that these last two survey follow-ups are completely web-based and given this unprecedented Coronavirus (COVID-19) pandemic it is even more important to implement innovative ideas in retaining participants. Our hope is that this strategy will encourage those participants who are slow to respond and will enhance the likelihood for more web survey completions to improve study response rates, which is critical for the success of the study.

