data collection) that if a student becomes upset, they should offer them the option of discontinuing the survey without penalty (i.e., still receiving gift card) or continuing at a later time. Furthermore, the tailored survey administration limits student exposure to potentially sensitive items: students without a history of dating are not exposed to TDV questions; similarly, students who have not engaged in sexual behavior are not exposed to more-detailed questions about number of sexual partners or condom use. All students will also be instructed that they may skip any item that makes them feel uncomfortable. In the event of any emotional distress, research staff will remain with the student until he or she is no longer distressed. [name] will be available at all times to provide immediate supervision or to counsel students. Students who wish to pursue additional therapy will be given a referral list specifically tailored to his or her request. We will have prepared referral lists for TDV perpetration and victimization, as well as for other psychological problems. At the end of each assessment, all students will be offered a list of referrals and a teen safety plan designed specifically for adolescents in violent relationships. Of note, we have established connections with local organizations that will be available to provide counseling to participants if needed. We will not be asking about suicide as part of the program, so it is unlikely that we will have to deal with this issue. However, anyone having direct involvement with the students will be fully trained by [name] in procedures for assessing and intervening in cases where suicidal ideation is expressed. Research staff will be instructed to immediately contact [name] and the project director if suicidal ideation is expressed. Appropriate clinical action will be taken in these circumstances, including hospitalization and/or referral to another level of clinical care.

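### The distress procedure is worded for in-person surveys, but about half of planned assessments take place outside school, and a remote student who stops early is not described as receiving the referral materials at that sitting

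*Combined protocol and SAP*

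**What the plan says.** All references are to the combined protocol and SAP.

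**Distress procedure (Protection against Risk).** The section accepts that the assessments may upset students. Research staff, expressly including those of the survey contractor, are told to offer an upset student the choice of stopping, with the gift card still paid, or of carrying on another time. If there is distress, "research staff will remain with the student until he or she is no longer distressed". For everyone, "At the end of each assessment, all students will be offered a list of referrals and a teen safety plan". The section also provides for:
- permission to skip any item;
- a filter that withholds the dating-violence items from students who have not dated;
- a tailored referral list on request, with no time point given;
- a clinician available at all times;
- links with local counseling organizations;
- a separate clinical protocol for more severe cases.

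**Setting and mode.** Under Data Collection Procedures, "Baseline and the 1-year follow-up will be conducted in the schools using paper and pencil surveys or school computers for web-based surveys". Students not reached there at 1 year complete the survey elsewhere by web, telephone or paper. For the later waves, "the 2- and 3-year follow-ups will be done outside of the school setting via the mixed-mode approach". The section on Follow-up, Tracking, and Retention has the contractor "conservatively estimate that approximately 80% will be at the same school" at 1 year, and later says that "these last two survey follow-ups are completely web-based". Sampling Design and Rationale also describes the last two waves as web surveys.

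**The concern.** The active part of the procedure depends on a person: someone must notice that the student is upset, make the offer and stay. The data collection plan removes that person from a large share of assessments, and no version of the procedure for web, paper or telephone is given. The sections also differ on mode for the last two waves (wholly web in one place, mixed mode in another), so the reader cannot tell how many remote students would have an interviewer on the line.

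The participants are minors answering questions on violence and sexual behavior. Three features make the remote waves the place where the procedure most needs to be explicit:
- The universal materials are tied to the end of the survey, and a student may stop because of the items that come before it.
- The no-penalty assurance is something that staff offer. Elsewhere the follow-up gift cards, service hours and lottery entry are tied to completing the survey. A remote student who stops is not described as being told that the gift card is still paid.
- The school counselor route is described for the middle schools, and by the 2- and 3-year surveys participants have moved to high school.

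There is also a consequence for safety reporting. Where distress is unlikely to be observed, few or no reported events at those waves would be weak evidence that the surveys caused none.

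**Working it through.** **Step 1. Share of assessments outside school.** The plan states no such share, so there is no figure to reproduce. It can be counted from these inputs:
- Students: 3,000 (Sampling Design and Rationale: "Students (N=3,000) in these schools will be the unit of analysis").
- Assessments per student: 4 (Research Design: "Outcomes will be assessed at baseline and at 12, 24, and 36 months post intervention").
- Baseline: all in school.
- 12 months: about 80% in school, so about 20% outside.
- 24 and 36 months: all outside school.
- Retention r1, r2, r3 at 12, 24 and 36 months: no rate is given, so a range is assumed.

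Remote share = (0.20·r1 + r2 + r3) / (1 + r1 + r2 + r3).

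At full retention, remote = 0.20 × 3,000 + 3,000 + 3,000 = 6,600, total = 4 × 3,000 = 12,000, and the share is 6,600 / 12,000 = 55%.

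| Assumed retention at 12/24/36 months | Remote | Total | Share |
|---|---|---|---|
| 100/100/100% | 6,600 | 12,000 | 55.0% |
| 90/90/90% | 5,940 | 11,100 | 53.5% |
| 80/80/80% | 5,280 | 10,200 | 51.8% |
| 70/70/70% | 4,620 | 9,300 | 49.7% |
| 90/80/70% | 5,040 | 10,200 | 49.4% |
| 50/50/50% | 3,300 | 7,500 | 44.0% |
| 80/60/50% | 3,780 | 8,700 | 43.4% |

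The plan calls its 80% conservative. In the limit where every 12-month survey is done in school, the share is 6,000 / 12,000 = 50% at full retention, and 3,300 / 8,700 = 38% in the last row.

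**Step 2. Each safeguard against each remote mode.**

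| Safeguard | Self-completed web or paper | Telephone |
|---|---|---|
| Staff notice upset | No observer | Possible by ear |
| Staff offer to stop or resume without penalty | Nobody to make the offer; no on-screen or printed version described | Possible |
| Staff stay with the student | Not possible | Only by staying on the line, which the text does not state |
| Referral list and safety plan at the end | Reached by completers; not described for early stoppers | Delivery not described |
| Item skipping; dating-history filter | Works | Works |
| Tailored list on request; clinician available | No route for a remote student described | Could be asked for on the call |

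In self-completed surveys, all three staff steps fail as written. The safeguards that still work reduce exposure to upsetting items; they do not respond to distress already felt.

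**The case against.** The best defence is that this is a summary protocol which does not distinguish modes, and that much of the protection survives. Most of that is fair:
- Telephone is an allowed mode, and the stop-or-resume instruction is addressed to the contractor's staff. The mode split is not given, so the 6,600 remote assessments are not 6,600 unobserved ones.
- Item skipping and the dating-history filter work in every mode.
- The universal materials are due at every assessment, including the in-school baseline. A student who stops early in 9th grade should, on the plan, already have been offered them at least once.
- The severe-case protocol and the draft survey are mentioned but are not in the public document. Either could contain remote provisions, and their absence is not counted against the plan.
- The sponsor expects mostly mild discomfort and reports no adverse events in its previous studies. No distress rate is available to set against this.

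A reader might infer that the procedure fails in every remote assessment, or that referrals of any kind arrive only at the end of the survey. The documents support neither. Telephone contact leaves part of the procedure workable, and the tailored list has no time point. Nor does the general rule require staff to call the clinician; immediate contact is specified only when suicidal ideation is expressed.

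What remains is narrower. For self-completed web and paper surveys, the text does not say how distress comes to anyone's notice, who responds, or how the materials reach a student who stops early. A protocol for severe cases would not, by its description, cover the milder cases that the sponsor expects most often.

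**Conclusion.** The point holds in this limited form. The distress procedure is written for in-person administration, while about half of planned assessments are outside school: 55% at full retention, and about 43% to 55% over the assumed retention patterns with 80% of 12-month surveys in school. As written, its staff-dependent steps cannot operate in self-completed web or paper surveys, and a student who stops such a survey early is not described as receiving the universal referral list and safety plan at that sitting.

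The size rests on the plan's own enrolment, wave and 80% figures and on assumed retention. It measures assessments outside school, not distress events or unobserved students, neither of which the documents allow to be counted. It would be too strong to say that a lack of adverse events at the remote waves carries no information, since students could still report through the contractor; it carries little. The point concerns participant protection and does not bear on the primary effect estimate.

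**What to change.** 1. Reconcile Protection against Risk with Sampling Design and Rationale, Data Collection Procedures, and Follow-up, Tracking, and Retention. The distress procedure should state how it applies to web, paper and telephone, and the sections should agree on the mode of the last two waves. If the severe-case protocol already covers remote students, a cross-reference would settle that part.
2. In the remote web survey, make the existing referral list, the existing safety plan and the no-penalty stop-or-resume statement available from the start and on the screen reached on early exit, as well as at the end. Put the same material at the front of paper surveys.

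How distress is handled clinically, and by whom, is for the sponsor to state.

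The cost is minor survey programming and an IRB amendment. The Measures section already plans for dynamic surveys, and the materials exist. A more visible option to stop may slightly raise the number of partial completions.
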